4.2 Scientific rationale for study design

Overall rationale and study population:

The purpose of this study is to explore the efficacy of using a functional method of calling HRR deficiency (HRD) to predict response to olaparib. Men with mCRPC will be eligible if they have a positive LOH score on metastatic tissue and/or cell-free circulating tumor DNA (ctDNA), which has been associated with response to PARP inhibition¹⁰. They are eligible for inclusion into the study if they have progressed on abiraterone or enzalutamide, which is in concordance with the current population for which olaparib is indicated.

Study design:

This is a single arm, Phase II study designed to provide an initial estimate of clinical activity of olaparib in mCRPC patients that have iHRD+ tumors. Because there is no control group this study will not be blinded.

Primary and secondary outcome measures:

Lowest on-treatment PSA was chosen as a primary endpoint, as decline in PSA is generally associated with tumor control and can be assessed as early as 12 weeks. Radiographic response rate was not chosen as many prostate cancer patients have primarily osseous metastases and are not evaluable per RECIST criteria. This study follows the PCWG3 criteria for assessing PSA and defining PSA progression¹. Secondary outcomes included are also reflective of PCWG3 guidelines.

4.3 Justification for dose

The dose of olaparib used in this study is 300 mg twice daily, which is the currently FDA approved dose.

4.4 End of study definition

The end of study is defined as the last expected visit/contact of the last patient undergoing the study. Follow up will continue for up to one year after the last patient discontinues treatment.

5. STUDY POPULATION

Each patient should meet all of the inclusion criteria and none of the exclusion criteria for this study in order to be assigned to a study intervention. Under no circumstances can there be exceptions to this rule. Patients who do not meet the entry requirements are screen failures, refer to section 5.4.

5.1 Inclusion criteria

Patients are eligible to be included in the study only if all of the following inclusion criteria and none of the exclusion criteria apply:

1. Capable of giving signed informed consent which includes compliance with the requirements and restrictions listed in the informed consent form (ICF) and in this protocol.
2. Subject must be \geq 18 years of age at the time of signing the informed consent form.
3. Individuals who have documented histologically confirmed adenocarcinoma of the prostate.
4. Subject must have evidence of castration resistant prostate cancer as evidenced by PSA progression (per Prostate Cancer Working Group 3 [PCWG3] criteria) and a castrate serum testosterone level (i.e. \leq 50 mg/dL)¹.
5. PSA must be at least 2 ng/mL and rising on two successive measurements at least two weeks apart.
6. At least one lesion (measurable and/or non-measurable) that can be accurately assessed at baseline by CT scan, MRI, or PET and is suitable for repeated assessment.
7. Must have progressed on abiraterone and/or a second-generation AR antagonist (i.e. enzalutamide, apalutamide, or darolutamide). If these were given in the hormone sensitive setting, patients must also have progressed on at least one prior approved therapy for CRPC.
8. Must have archival tissue available or be willing to undergo metastatic biopsy in order to perform next-generation DNA sequencing and undergo whole exome sequencing.
9. Patient must have a positive LOH score on prior UW OncoPlex testing

10. Patients must have normal organ and bone marrow function measured within 28 days prior to administration of study treatment as defined below:

- Hemoglobin ≥ 10.0 g/dL with no blood transfusion in the past 28 days
- Absolute neutrophil count (ANC) $\geq 1.5 \times 10^9$ /L
- Platelet count $\geq 100 \times 10^9$ /L
- Total bilirubin $\leq 1.5 \times$ institutional upper limit of normal (ULN)
- Aspartate aminotransferase (AST) (Serum Glutamic Oxaloacetic Transaminase (SGOT)) / Alanine aminotransferase (ALT) (Serum Glutamic Pyruvate Transaminase (SGPT)) $\leq 2.5 \times$ institutional upper limit of normal unless liver metastases are present in which case they must be ≤ 5 x ULN
- Patients must have creatinine clearance estimated of ≥ 51 mL/min using the Cockcroft-Gault equation or based on a 24 hour urine test:

$$\text{Estimated creatinine clearance} = \frac{(140 - \text{age [years]}) \times \text{weight (kg)}}{\text{serum creatinine (mg/dL)} \times 72}$$

11. Eastern Cooperative Oncology Group (ECOG) performance status ≤ 2

12. Patients must have an estimated life expectancy ≥ 16 weeks.

13. Male patients must use a condom during treatment and for 3 months after the last dose of olaparib when having sexual intercourse with a pregnant woman or with a woman of childbearing potential. Female partners of male patients should also use a highly effective form of contraception ([see appendix C for acceptable methods]) if they are of childbearing potential

5.2 Exclusion criteria

1. As judged by the investigator, any evidence of serious and/or unstable pre-existing medical or psychiatric condition which in the investigator's opinion makes it undesirable for the patient to participate in the trial.
2. Other malignancy unless curatively treated with no evidence of disease for ≥ 5 years except: adequately treated non-melanoma skin cancer and non-muscle invasive bladder cancer.
3. Resting ECG indicating uncontrolled, potentially reversible cardiac conditions, as judged by the investigator (e.g., unstable ischemia, uncontrolled symptomatic arrhythmia, congestive heart failure, QTcF prolongation >500 ms, electrolyte disturbances, etc.), or patients with congenital long QT syndrome.

4. Persistent toxicities (>Common Terminology Criteria for Adverse Event (CTCAE) grade 2) caused by previous cancer therapy, excluding alopecia.
5. Patients with myelodysplastic syndrome/acute myeloid leukemia or with features suggestive of MDS/AML.
6. Patients with symptomatic uncontrolled brain metastases. A scan to confirm the absence of brain metastases is not required. The patient can receive a stable dose of corticosteroids before and during the study as long as these were started at least 4 weeks prior to treatment. Patients with spinal cord compression unless considered to have received definitive treatment for this and evidence of clinically stable disease for 28 days.
7. Patients considered a poor medical risk due to a serious, uncontrolled medical disorder, non-malignant systemic disease or active, uncontrolled infection. Examples include, but are not limited to, uncontrolled ventricular arrhythmia, recent (within 3 months) myocardial infarction, uncontrolled major seizure disorder, unstable spinal cord compression, superior vena cava syndrome, extensive interstitial bilateral lung disease on High Resolution Computed Tomography (HRCT) scan or any psychiatric disorder that prohibits obtaining informed consent.
8. Patients unable to swallow orally administered medication and patients with gastrointestinal disorders likely to interfere with absorption of the study medication.
9. Immunocompromised patients, e.g., patients who are known to be serologically positive for human immunodeficiency virus (HIV) and are not receiving active treatment or have a detectable viral load.
10. Patients with known active hepatitis (i.e. Hepatitis B or C).
 - Active hepatitis B virus (HBV) is defined by a known positive HBV surface antigen (HBsAg) result. Patients with a past or resolved HBV infection (defined as the presence of hepatitis B core antibody and absence of HBsAg) are eligible.
 - Patients positive for hepatitis C virus (HCV) antibody are eligible only if polymerase chain reaction is negative for HCV RNA.
11. Any previous treatment with PARP inhibitor, including Olaparib.
12. Any previous treatment with platinum chemotherapy in the metastatic castration-resistant setting.
13. Patients receiving any systemic chemotherapy or radiotherapy (except for palliative reasons) within 3 weeks prior to study treatment.

14. Concomitant use of known strong CYP3A inhibitors (eg. itraconazole, telithromycin, clarithromycin, protease inhibitors boosted with ritonavir or cobicistat, indinavir, saquinavir, nelfinavir, boceprevir, telaprevir) or moderate CYP3A inhibitors (eg. ciprofloxacin, erythromycin, diltiazem, fluconazole, verapamil). The required washout period prior to starting olaparib is 2 weeks.
15. Concomitant use of known strong (eg. phenobarbital, enzalutamide, phenytoin, rifampicin, rifabutin, rifapentine, carbamazepine, nevirapine and St John's Wort) or moderate CYP3A inducers (eg. bosentan, efavirenz, modafinil). The required washout period prior to starting olaparib is 5 weeks for enzalutamide or phenobarbital and 3 weeks for other agents.
16. Major surgery within 2 weeks of starting study treatment and patients must have recovered from any effects of any major surgery.
17. Previous allogenic bone marrow transplant or double umbilical cord blood transplantation (dUCBT).
18. Patients with a known hypersensitivity to olaparib or any of the excipients of the product.
19. Involvement in the planning and/or conduct of the study.
20. Judgment by the investigator that the patient should not participate in the study if the patient is unlikely to comply with study procedures, restrictions and requirements.

5.3 Lifestyle restrictions

No restrictions are required.

5.3.1 Meals and dietary restrictions

It is prohibited to consume grapefruit juice while on olaparib therapy.

5.3.2 Activity

Contraception

Male patients must use a condom during treatment and for 3 months after the last dose of olaparib when having sexual intercourse with a pregnant woman or with a woman of childbearing potential. Female partners of male patients should also use a highly effective form of contraception (as described in Appendix C) if they are of childbearing potential. Male patients should not donate sperm throughout the period of taking olaparib and for 3 months following the last dose of olaparib.

For details of acceptable methods of contraception refer to Appendix C Acceptable Birth Control Methods.

5.4 Screen failures

Screen failures are defined as patients who signed the informed consent form to participate in the clinical study but are not subsequently entered in the study. Minimal information includes demography, screen failure details, eligibility criteria, and any serious adverse event (SAE).

Individuals who do not meet the criteria for participation in this study (screen failure) may be rescreened.

These patients should have the reason for study withdrawal recorded in the CRF.

5.5 Study Treatments

Study treatment is defined as any investigational product(s) (including marketed product comparator and placebo) or medical device(s) intended to be administered to a study participant according to the study protocol. Study treatment in this study refers to the drug olaparib.

Treatments administered

5.5.1 Investigational products

Table 2 **Study Treatments**

Treatment 1	
Study treatment name:	Olaparib
Dosage formulation:	Tablets
Route of administration	Oral
Dosing instructions:	Olaparib tablets should be taken at the same time each day, approximately 12 hours apart with one glass of water. The tablets should be swallowed whole and not chewed, crushed, dissolved or divided. Olaparib tablets can be taken with or without food.
Packaging and labelling	Study treatment will be provided in high-density polyethylene (HDPE) bottles with child-resistant closures. Each container will be labeled in accordance with Good Manufacturing Practice (GMP) Annex 13 and per country regulatory requirement.

If vomiting occurs shortly after the olaparib tablets are swallowed, the dose should only be replaced if all of the intact tablets can be seen and counted. Should any patient enrolled on the study miss a scheduled dose for whatever reason (e.g., as a result of forgetting to take the tablets or vomiting), the patient will be allowed to take the scheduled dose up to a maximum of 2 hours after that scheduled dose time. If greater than 2 hours after the scheduled dose time, the missed dose is not to be taken and the patient should take their allotted dose at the next scheduled time.

5.6 Preparation/handling/storage/accountability

The investigator or designee must confirm appropriate temperature conditions have been maintained during transit for all study treatment received and any discrepancies are reported and resolved before use of the study treatment.

Only patients enrolled in the study may receive study treatment and only authorized site staff may dispense study treatment. Lynparza will be supplied from commercial stock, as bulk supplies to a single site only. The Sponsor will be responsible for labelling and onward distribution to sub-sites if applicable. At site, all study treatments must be stored in a secure, environmentally controlled, and monitored (manual or automated) area in accordance with the labelled storage conditions with access limited to the investigator and authorized site staff.

The investigator, institution, or the head of the medical institution (where applicable) is responsible for study treatment accountability, reconciliation, and record maintenance (i.e., receipt, reconciliation, and final disposition records).

5.7 Treatment compliance

Patients should be given clear instructions on how and when to take their study treatment. Patients will self-administer olaparib. They will receive a pill diary as shown in Appendix D. Study site staff will make tablet counts at regular intervals during treatment. After the tablet count has been performed, the remaining tablets will not be returned to the patient but will be retained by the investigative site until reconciliation is completed by the study monitor. All patients must return their bottle(s) of olaparib at the appropriate scheduled visit, when a new bottle will be dispensed. Patients will be instructed to notify study site personnel of missed doses.

Any change from the dosing schedule, dose interruptions, dose reductions, dose discontinuations should be recorded in eCRF.

The Investigational Product Storage Manager is responsible for managing the IMP from receipt by the study site until the destruction or return of all unused IMP. The Investigator(s) is responsible for ensuring that the patient has returned all unused IMP.

5.8 Concomitant therapy

The use of any natural/herbal products or other traditional remedies should be discouraged, but use of these products, as well as any medication or vaccine including over-the-counter or

prescription medicines, vitamins, and/or herbal supplements that the patient is receiving at the time of enrolment or receives during the study must be recorded along with:

- Reason for use
- Dates of administration including start and end dates
- Dosage information including dose and frequency

Anti-emetics/Anti-diarrheals

From screening part 2 onwards, should a patient develop nausea, vomiting and/or diarrhea, then these symptoms should be reported as AEs (see section 8.3) and appropriate treatment of the event given.

Medications that may NOT be administered

Table 4 Prohibited medications

Prohibited medication/class of drug:	
Anticancer therapy:	Not permitted while the patient is receiving study medication
Chemotherapy	
Immunotherapy	
Radiotherapy (except palliative)	
Biological therapy	
Other novel agents	
Live virus vaccines	Not permitted while the patient is receiving study medication and during the 30 day follow up period.
Live bacterial vaccines	An increased risk of infection by the administration of live virus and bacterial vaccines has been observed with conventional chemotherapy drugs and the effects with olaparib are unknown.

Table 5 **Restricted concomitant medications**

Medication/class of drug:	Usage (including limits for duration permitted and special situations in which it's allowed):
Strong CYP3A inhibitors: itraconazole, telithromycin, clarithromycin, boosted protease inhibitors, indinavir, saquinavir, nelfinavir, boceprevir, telaprevir	Strong or moderate CYP3A inhibitors should not be taken with olaparib. If there is no suitable alternative concomitant medication then the dose of olaparib should be reduced for the period of concomitant administration. The dose reduction of olaparib should be recorded in the CRF with the reason documented as concomitant CYP3A inhibitor use.
Moderate CYP3A inhibitors: ciprofloxacin, erythromycin, diltiazem, fluconazole, verapamil	
 • Strong CYP3A inhibitors – reduce the dose of olaparib to 100 mg twice daily for the duration of concomitant therapy with the strong inhibitor and for 5 half-lives afterwards. • Moderate CYP3A inhibitors - reduce the dose of olaparib to 150 mg twice daily for the duration of concomitant therapy with the moderate inhibitor and for 3 half-lives afterwards. • After the washout of the inhibitor is complete, the olaparib dose can be re-escalated.
Strong inducers: phenobarbital, phenytoin, rifampicin, rifabutin, rifapentine, carbamazepine, nevirapine, enzalutamide and St John's Wort	Strong or moderate CYP3A inducers should not be taken with olaparib. If the use of any strong or moderate CYP3A inducers are considered necessary for the patient's safety and welfare this could diminish the clinical efficacy of olaparib.
Moderate CYP3A inducers: bosentan, efavirenz and modafinil	If a patient requires use of a strong or moderate CYP3A inducer then they must be monitored carefully for any change in efficacy of olaparib.

Table 5 **Restricted concomitant medications**

Medication/class of drug:	Usage (including limits for duration permitted and special situations in which it's allowed):

 • CYP3A4 substrates with narrow therapeutic margin: cisapride, cyclosporine, ergot alkaloids, fentanyl, pimozide, sirolimus, and tacrolimus • CYP2B6 substrates: bupropion, efavirenz • OATP1B1 substrates: bosentan, glibenclamide, repaglinide, statins and valsartan • OCT1, MATE1 and MATE2K substrates: metformin • OCT2 substrates: serum creatinine • OAT3 substrates: furosemide, methotrexate • BCRP substrates: methotrexate, rosuvastatin • P-gp substrates: simvastatin, pravastatin, dabigatran, digoxin and colchicine 	
Effect of olaparib on other drugs
 
Based on limited in vitro data, olaparib may increase the exposure to substrates of CYP3A4, OATP1B1, OCT1, OCT2, OAT3, MATE1 and MATE2K.
 
Based on limited in vitro data, olaparib may reduce the exposure to substrates of 2B6.
 
Caution should be observed if statins or sensitive CYP3A4 substrates are co-administered.
 
Appropriate clinical monitoring is recommended for patients receiving P-gp substrates or CYP3A substrates with a narrow therapeutic margin concomitantly with olaparib.

Anticoagulant therapy	
Patients who are taking warfarin may participate in this trial; however, it is recommended that international normalised ratio (INR) be monitored carefully at least once per week for the first month, then monthly if the INR is stable. Non-vitamin K antagonist oral anticoagulants (NOACs), subcutaneous heparin and low molecular weight heparin may be given concomitantly with olaparib and INR monitoring is not required. If NOACs are used, it is preferable to avoid CYP3A substrates (e.g apixaban and rivaroxaban) if possible.

Table 5 Restricted concomitant medications

Medication/class of drug:	Usage (including limits for duration permitted and special situations in which it's allowed):
Palliative radiotherapy	Palliative radiotherapy may be used for the treatment of pain at the site of bony metastases that were present at baseline, provided the investigator does not feel that these are indicative of clinical disease progression during the study period. Study treatment should be discontinued for a minimum of 3 days before a patient undergoes therapeutic palliative radiation treatment. Study treatment should be restarted within 4 weeks as long as any bone marrow toxicity has recovered.
Administration of other anti-cancer agents	Patients must not receive any other concurrent anti-cancer therapy, including investigational agents, while on study treatment. Patients may continue the use of bisphosphonates or denosumab for bone disease and corticosteroids for the symptomatic control of brain metastases provided the dose is stable before and during the study and they were started at least 4 weeks prior to beginning study treatment.

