5.9 Dose modification

Dose Reductions

In case a dose reduction is necessary, the Study treatment will be administered as follows:

Table 6 Dose reductions for olaparib to manage adverse events

Initial Dose	Following re-challenge post interruption: Dose reduction 1	Dose reduction 2
300 mg twice daily	250 mg twice daily	200 mg twice daily

Table 7 Dose reduction for olaparib if patient develops moderate renal impairment

Initial Dose	Moderate renal impairment (calculated creatinine clearance by Cockcroft -Gault equation or based on a 24 hour urine test between 31 and 50 ml/min): Dose reduction
300 mg twice daily	200 mg twice daily

Table 8 Dose reductions for olaparib if patient has to start taking a strong or moderate CYP3A inhibitor

Initial Dose	Strong CYP3A inhibitor	Moderate CYP3A inhibitor
300 mg twice daily	100 mg twice daily	150 mg twice daily

For guidance on dose reductions for management of AEs (including renal impairment) refer to section 6.5.

For guidance on dose reductions when concomitant strong or moderate CYP3A inhibitors cannot be avoided see section 6.5.

When dose reduction is necessary patients will take one 150 mg tablet and one 100 mg tablet twice daily or two x 100 mg tablet twice daily (see Section 8.4.6), or one 150 mg tablet twice daily or one 100 mg tablet twice daily (see Section 6.5).

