6.5.3 Overdose

There is currently no specific treatment in the event of overdose with olaparib and possible symptoms of overdose are not established.

Olaparib must only be used in accordance with the dosing recommendations in this protocol. Any dose or frequency of dosing that exceeds the dosing regimen specified in this protocol should be reported as an overdose. The Maximum Tolerated Dose is 300 mg twice daily (tablet).

Adverse reactions associated with overdose should be treated symptomatically and should be managed appropriately.

- An overdose with associated AEs is recorded as the AE diagnosis/symptoms on the relevant AE modules in the CRF.

For overdoses associated with a SAE, the standard reporting timelines apply, see Section 6.4.2. For other overdoses, reporting must occur within 30 days.

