6.5.5 Management of adverse events

Any toxicity observed during the course of the study could be managed by interruption of the dose of study treatment or dose reductions. Repeat dose interruptions are allowed as required, for a maximum of 4 weeks on each occasion. Study treatment can be dose reduced to 250 mg twice daily as a first step and to 200 mg twice daily as a second step. If the reduced dose of 200 mg twice daily is not tolerable, no further dose reduction is allowed, and study treatment should be discontinued.

Once dose is reduced, escalation is not permitted (except following concomitant treatment with CYP3A4 inhibitors – see Section 6.5

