6.5.5.3 Renal impairment

If subsequent to study entry and while still on study therapy, a patient's estimated CrCl falls below the threshold for study inclusion (≥ 51 ml/min), retesting should be performed promptly.

A dose reduction is recommended for patients who develop moderate renal impairment (calculated creatinine clearance by Cockcroft-Gault equation or based on a 24 hour urine test of between 31 and 50 ml/min) for any reason during the course of the study: the dose of olaparib should be reduced to 200 mg twice daily.

Because the CrCl determination is only an estimate of renal function, in instances where the CrCl falls to between 31 and 50 mL/min, the investigator should use his or her discretion in determining whether a dose change or discontinuation of therapy is warranted.

Olaparib has not been studied in patients with severe renal impairment (creatinine clearance ≤ 30 ml/min) or end-stage renal disease; if patients develop severe impairment or end stage disease is it recommended that <<select olaparib or study treatment>> be discontinued.

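### Table 5 sets olaparib at 150 mg twice daily with any moderate CYP3A inhibitor, so a man already reduced to 200 mg gets a 25% cut where a man on 300 mg gets 50%

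*Combined protocol and SAP*

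**What the plan says.** **Inhibitor doses.** Section 5.8, Table 5, says inhibitors should be avoided, and then: "If there is no suitable alternative concomitant medication then the dose of olaparib should be reduced for the period of concomitant administration". For a moderate inhibitor the instruction is to "reduce the dose of olaparib to 150 mg twice daily for the duration of concomitant therapy with the moderate inhibitor"; for a strong one, to "reduce the dose of olaparib to 100 mg twice daily for the duration of concomitant therapy with the strong inhibitor". Neither instruction depends on the dose the man is taking. After washout the dose may go back up, but Table 5 does not say to what level.

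**Table 8.** Section 5.9, Table 8, is titled "Dose reductions for olaparib if patient has to start taking a strong or moderate CYP3A inhibitor". It has one row, starting from 300 mg twice daily, and gives the same 150 mg and 100 mg. There is no row for 250 or 200 mg. Section 5.9 refers to Section 6.5 for more on inhibitor dosing, but Section 6.5 gives no inhibitor dose.

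**Reduced doses.** Table 6 and Section 6.5.5 take a man with toxicity from 300 to 250 and then 200 mg twice daily. At 200 mg there is no lower step, and if he cannot tolerate it he stops. Table 7, "Dose reduction for olaparib if patient develops moderate renal impairment", also leads to 200 mg. Section 6.5.5.3 says "the dose of olaparib should be reduced to 200 mg twice daily" and then leaves the decision partly to the investigator.

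**Re-escalation.** Section 6.5.5 states: "Once dose is reduced, escalation is not permitted (except following concomitant treatment with CYP3A4 inhibitors", followed by a pointer to Section 6.5.

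**The concern.** The protocol makes two kinds of dose reduction, one for the man's condition (toxicity or renal function) and one for an interacting drug, and nowhere says how they combine. Read literally, the inhibitor dose replaces the reduced dose and takes no account of it. The smaller proportional cut then goes to men who did not tolerate 300 mg or whose renal function has declined.

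What is at stake is patient safety. For the length of the inhibitor course, a man at the lowest permitted toxicity dose could be returned to about the exposure that led to his reductions. Table 5 puts no limit on how long that course may last.

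**Working it through.** **Inputs**
- Starting dose: 300 mg twice daily (Section 4.3, Table 8).
- Dose with a moderate inhibitor: 150 mg twice daily (Tables 5 and 8).
- Dose with a strong inhibitor: 100 mg twice daily (Tables 5 and 8).
- Toxicity steps: 250, then 200 mg (Table 6, Section 6.5.5).
- Moderate renal impairment: 200 mg (Table 7, Section 6.5.5.3).
- Tablets named for reductions: 100 mg and 150 mg (Section 5.9), not to be divided (Table 2).

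**Step 1. Size of the cut, from the doses alone.** Cut = 1 − (inhibitor dose ÷ current dose).
- Moderate inhibitor, man on 300 mg: 1 − 150/300 = 50%, the case Table 8 covers.
- Moderate inhibitor, man on 200 mg: 1 − 150/200 = 25%.
- Strong inhibitor: 1 − 100/300 = 67% from 300 mg, and 1 − 100/200 = 50% from 200 mg.

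This step needs no pharmacokinetic assumption.

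**Step 2. What it could mean for exposure.** The documents give no exposure figures. Assume exposure is proportional to dose, and let f be the factor by which a moderate inhibitor raises it. Relative to the man's own reduced level,

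ratio = (150 × f) ÷ 200 = 0.75 × f.

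If the cut from 300 to 150 mg is meant to hold exposure level, then f = 300/150 = 2. The ratio is 0.75 × 2 = 1.5, or +50%. In full-dose terms, a man reduced for toxicity is at 150 × 2 = 300 mg-equivalent, the level he was cut from. For a man reduced for renal impairment, the renal effect appears above and below the line and cancels, provided the inhibitor acts on him to the same degree. The +50% over his own level therefore also applies to him.

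**Step 3. Break-even and range.** The ratio passes 1 when f exceeds 200/150 = 1.33. Taking f from 1.5 to 2.5 as an assumed range, for a man on 200 mg after toxicity:

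| f | 150 mg (Table 5) | against 200 | 100 mg (proposed) | against 200 |
|---|---|---|---|---|
| 1.5 | 225 | +12.5% | 150 | −25% |
| 2.0 | 300 | +50% | 200 | 0% |
| 2.5 | 375 | +87.5% | 250 | +25% |

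**Step 4. Can the same proportional cut be dispensed?**
- 200 mg, moderate inhibitor: 200/2 = 100 mg, a listed tablet.
- 250 mg, moderate inhibitor: 250/2 = 125 mg, which cannot be made from these tablets. At f = 2, 100 mg gives 200 mg-equivalent (200/250, −20%) and 150 mg gives 300 (300/250, +20%).
- 200 mg, strong inhibitor: 200/3 = 67 mg, which cannot be made.

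Only the first case has a clean answer.

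**The case against.** The strongest reply is that the situation is rare and already supervised. Exclusion 14 bars moderate and strong inhibitors at entry with a two-week washout, naming diltiazem and verapamil, so only an inhibitor started on study counts. Even then Table 5 requires that no suitable alternative exists, and the man must already be on a reduced dose. The renal case also needs a fall in clearance after entry, which requires at least 51 mL/min. Concomitant medication and blood counts are reviewed each cycle, and Section 6.3.1 allows extra safety samples. All of this stands and keeps the point small. It does not supply the missing dose.

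It can also be said that Table 8 is silent on reduced men and does not direct them to 150 mg. That is a fair reading of Table 8, but Table 5 carries no such limit.

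The exposure factor is inferred, and the 150 mg dose may partly reflect the tablet strengths available. That also stands. The 25% against 50% difference does not depend on it; the +50% does.

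A reader might go further in three ways that the documents do not support:
- **Renal impairment and the maximum tolerated dose.** Multiplying 150 × 2 × 1.5 (the last from 300/200 in Table 7) gives 450 mg-equivalent, which seems to exceed the 300 mg maximum tolerated dose in Section 6.5.3. That needs two inferred factors to multiply, and it sets an exposure equivalent against an administered tablet dose. With a moderate factor of 1.5 and an assumed renal factor of 1.2, the result is 150 × 1.5 × 1.2 = 270, below 300.
- **Conflict with the no-escalation rule.** Going from 200 to 150 mg lowers the dose given, so Section 6.5.5 is not contradicted.
- **New fixed rules for men on 250 mg, or compulsory interruption with a strong inhibitor.** Step 4 shows that the first trades about 20% under against 20% over. For the second, a strong factor of 2 would leave a man on 200 mg exactly at his level (100 × 2 = 200), so stopping treatment for everyone is not justified.

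**Conclusion.** The point holds for a man on 200 mg twice daily who must start a moderate inhibitor. As written, Table 5 cuts his dose by 25% where a man on 300 mg is cut by 50%. If the inhibitor about doubles exposure, he is about 50% above his reduced level (+12.5% to +87.5% for a 1.5- to 2.5-fold rise), and a toxicity-reduced man is back near the 300 mg level. Below a 1.33-fold rise there is no excess. These exposure figures assume proportionality to dose and a factor inferred from the protocol's own dose cut.

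The documents do not say how many of the 30 planned patients would be affected, and the number is probably small. This is a gap in the dosing tables with a cheap remedy; it has no bearing on sample size, power or the primary analysis.

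**What to change.** At the next amendment, add to Tables 5 and 8:
1. A man already on 200 mg twice daily, for toxicity or moderate renal impairment, who must start a moderate CYP3A inhibitor takes 100 mg twice daily during the inhibitor course and the washout already specified.
2. After washout he returns to the dose he was on before the inhibitor, not to 300 mg. This also settles the target that Table 5 and the exception in Section 6.5.5 leave open.

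For a strong inhibitor in a man on a reduced dose, leave the decision to hold olaparib to the investigator. No new rule is proposed for men on 250 mg.

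The cost is one row and a sentence or two, using a listed tablet, with no extra patients, visits or procedures. The downside is some under-exposure if the inhibitor effect is less than 2-fold: at 1.5-fold, 150 mg-equivalent against 200. Because the factor is inferred, the sponsor should check the 100 mg dose against the current Investigator Brochure before adopting it.
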